7.4 Duration of therapy and Study Period

Treatment with tTF-NGR may continue until one of the following criteria applies:

disease progression

- intercurrent illness that prevents further administration of treatment according to the judgement of the Investigators
- ➤ Occurrence of Dose Limiting Toxicity (DLT), i.e., unacceptable adverse event(s), including Grade ≥ 3 (CTCAE) toxicity for any organ with the exception of the hematopoietic system or Grade 4 for the hematopoietic system attributed to the IMP
- patient decides to withdraw from the study
- general or specific changes in the patient's condition rendering the patient unfit for further treatment in the judgement of the Investigators
- patient is lost to follow-up
- death

Duration of Study Period with follow-up is defined as being

- > from day of signature of Informed Consent to
- day 5 after the start of the last dose level plus 3 months of observation

Patients will be removed from study treatment when any of the criteria listed under section 7.4 applies or the Study Period is completed.

In patients with objective response and good toleration on a specific dose-level reached, or with stable disease upon 8 cycles of therapy, individual dose-escalation will be stopped and patients will be further treated for up to 3 months with the specific dose under which response occurred, or in case of stable disease with the dose at the 8th cycle. If this patient is treated with dose-escalation steps, he/she will be replaced by the next patient to continue the dose-escalation. This is to not add further risk to an individual, when individual benefit is visible. Upon this time Study Period in these individual patients will end. These patients will be eligible for further compassionate-use treatment with the IMP on the dose-level after completion of the Study Period as long as they benefit from treatment in accordance with §34 of the Declaration of Helsinki (2013 Fortaleza, Brazil). Serious adverse events (see paragraph 13 of this protocol) occurring during compassionate use treatment will be reported as within the defined Study Period to guarantee patient safety within this trial.

8. Dosing delays and dose de-escalations in individual patients

De-escalation in individual patients in dosing is not allowed during the Study Period to not interfere with the description of Dose Limiting Toxicity (DLT) and MTD.

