When DLT is observed in the 1st patient, up to 5 more patients will be treated on the same dose level, or in case of deadly DLT in the dose level below (verification group for DLT; maximum of 6 patients on this level). Upon observation of no additional DLT after treating 6 patients on this dose level dose escalation can be resumed in one patient. The remaining 5 patients can be treated without dose-escalation until tumor progression or DLT. Upon observation of one more episode of any DLT within the verification group, patient accrual to this verification group is stopped with this second patient with DLT and de-escalation by a $0.5 \text{ mg/m}^2/\text{day}$ step is performed in 5 further patients until $\leq 1 \text{ DLT}$ occurs in 5 further patients treated on a specific dose-level, i.e. with $\leq 1/6$ patients in total with DLT on this dose level (scheme see below).

Maximum Tolerated Dose (MTD): MTD is the dose below the lowest dose level on which reproducible episodes of any DLT are observed. Reproducible episodes of DLT have also to be stated if DLT occurs in different organ systems of individual patients.

[figure not shown]
10. Dose escalation and de-escalation according to toxicity and dose recommended for phase II trials (RDPII)

The patients will be treated daily with tTF-NGR by 1-hour iv infusions for 5 days with MRI studies before, 4-6 hours after the 1st application, and on day 5 after treatment as decided by the Investigator.

[figure not shown]

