Starting dose will be 1 mg/m²/day. Intraindividual dose-escalation will be performed in 1 patient in 0.5 mg/m²/day steps (to a maximum of 8 cycles) upon a rest period of 16 days for the next treatment cycle of 5 days. The maximum number of 8 dose escalations is reached only if stable disease (SD) is ongoing upon 8 cycles of therapy. Dose-escalation is stopped before the maximum number of 8 escalation steps if tumor response, tumor progression or a Dose-Limiting Toxicity (DLT) is observed. If tumor response is observed or if a patient is diagnosed with progressive disease (PD) after ≥ 2 cycles or clinically as judged by the investigator even before 2 cycles, this patient will go off study and will be replaced by a further patient in whom individual dose escalation will be resumed, starting with the highest dose level reached without DLT in the previous patient. When any DLT is observed in this patient, intraindividual dose escalation is stopped and the patient is taken off study. In case of stable disease or response and resolution of the DLT this patient can be further treated on the highest tolerable dose level without DLT until any of the criteria under 7.4 is reached. This treatment will then be given on an individual compassionate-use basis (off study) according to § 34 of the Helsinki declaration (2013, Fortaleza; Post-Trial Provision).

If this first observed DLT is nonfatal, up to 5 more patients will then be treated on the same dose level having caused DLT (verification group). Patients of the verification group will be treated in sequence of each other, thus a patient has to tolerate the first cycle (5 days) and the rest period of 16 days without DLT before the next patient can be added to this verification group.

Upon observation of no additional DLT in the verification group in a minimum of 2 cycles for each patient, dose escalation can be resumed in one patient out of these until DLT (continue as above). The remaining patients in the verification group will be further treated at this dose-level until any of the criteria under 7.4 is reached.

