Upon observation of one more episode of any DLT within the first 2 cycles given to the patients in the verification group, patient accrual to this verification group is stopped with this second patient with DLT and de-escalation by a $0.5 \text{ mg/m}^2/\text{day}$ step is performed in further up to 5 patients. If on the next lower dose level there are $\geq 2 \text{ DLT}$ in 5 further patients (i.e., $\geq 2 \text{ DLT}$ in 6 patients in total on this dose level), de-escalation will continue. In case, patients of the verification group experience DLT in a later cycle (3rd and following), this will be counted as DLT with all consequences, although the procedure of the study was not influenced before such an event occurred.

Dose de-escalation will continue until ≤1 DLT occurs in 5 further patients treated on a specific dose-level, i.e. there are ≤1/6 patients with DLT in total on this dose level. This dose level is declared the MTD and will be recommended for further studies, such as phase II trials (RDPII).

If an observed DLT is fatal, the above dose escalation scheme is modified. Denote this dose d_{fatal} . In the unlikely event that further patients are treated with this dose, treatment in these patients will be stopped at this dose level and the investigator decides how to go on with the treatment in these patients. The next patients will not be treated with the dose d_{fatal} , but on the next lower dose level d_{fatal} - 0.5 mg/m²/day. If on the dose level d_{fatal} - 0.5 mg/m²/day no DLT or not more than 1 DLT is observed that is non-fatal, further patients are treated on the dose level d_{fatal} until any further DLT is observed or 6 patients are included on this dose level in total. Possible later dose escalation to a level at which one death occurred has to be discussed with the data safety board.

Only in the very unlikely event, that DLT occurs at the starting dose or the dose 0.5 mg/m²/day higher, further dose de-escalation below the starting dose level can be performed as described to establish MTD.

The above procedure is constructed so that MTD is defined similarly to a standard 3+3 design. I.e., any dose with observed DLT in $\leq 1/6$ patients is defined to be the MTD, if on the next higher dose level the observed number of patients with DLT is $\geq 2/6$. The following summary visualizes this procedure:

```

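### The cohort that sets the MTD and the phase II dose has no minimum DLT observation period, so a patient who leaves early counts as DLT-free

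*Combined protocol and SAP*

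**What the plan says.** **The rule that sets the primary endpoint.** Section 10: "Dose de-escalation will continue until ≤1 DLT occurs in 5 further patients treated on a specific dose-level". That level, with at most 1 of 6 patients affected in total, becomes the MTD and the dose recommended for phase II. Section 9 states the same criterion. Neither section says how long the five patients must be observed.

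**The 2-cycle decision point.** Section 10 writes it for the verification group, in both directions. To go up: "Upon observation of no additional DLT in the verification group in a minimum of 2 cycles for each patient, dose escalation can be resumed". To go down: "Upon observation of one more episode of any DLT within the first 2 cycles given to the patients in the verification group". It sets when a decision is taken and does not limit what is counted. For a DLT in cycle 3 or later in that group, section 10 says "this will be counted as DLT with all consequences". Section 9 describes the upward step without any cycle count: "Upon observation of no additional DLT after treating 6 patients on this dose level dose escalation can be resumed in one patient". It also limits a level to six patients.

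**Entry gate.** In the verification group, each patient must complete cycle 1 and the rest period without a DLT (5 + 16 = 21 days) before the next one enters (section 10).

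**Early exit and replacement.** Section 7.4 opens its list of reasons to stop with "Treatment with tTF-NGR may continue until one of the following criteria applies". The list includes progression, intercurrent illness, withdrawal and loss to follow-up. Replacement is described only for the patient in individual dose escalation. Section 10 has "this patient will go off study and will be replaced by a further patient in whom individual dose escalation will be resumed", section 16.1 is to the same effect, and section 7.4 has "If this patient is treated with dose-escalation steps, he/she will be replaced by the next patient to continue the dose-escalation". Section 17 asks only that the reason for premature termination be recorded. Section 16 defines no DLT-evaluable population.

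**The concern.** The authors treated two cycles as the exposure needed before acting on the verification group. The cohort that actually yields the MTD has no stated exposure requirement. Its denominator is simply patients treated, so someone who leaves after one DLT-free cycle, or after a single infusion, enters as a non-event. For any given five patients, cutting observation short can remove DLTs from the count but cannot add any. The error therefore runs one way, towards accepting the dose.

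In the verification group the consequence differs. Under section 10, an early leaver leaves the requirement of two cycles for each patient unmet, so escalation does not resume. That errs on the safe side, but the plan then offers no way forward: the level is limited to six patients and no replacement is foreseen. Section 9, which has no cycle count, would give a different answer.

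With five patients and a threshold of one DLT, a single classification can decide the MTD. If it is made after the data are seen, the choice of counting rule can become the choice of dose.

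**Working it through.** **1. The plan's own figure.** Section 16.1 counts 1 escalation patient with a DLT, 1 verification patient with a DLT and 5 de-escalation patients: 1 + 1 + 5 = 7. The stated minimum reproduces. It leaves no room for an unusable patient among the five.

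**2. Is early stopping foreseeable?** Two cycles take 2 × (5 + 16) = 42 days, which is 6 weeks. Section 6.1 requires a life expectancy of at least 6 weeks. With an assumed early-stop rate d per patient, the chance that at least one of five stops early is 1 − (1 − d)^5: 41%, 67%, 83% and 92% for d = 10%, 20%, 30% and 40%.

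**3. Effect on the decision.** The escalation patient normally passed the de-escalated level without a DLT, so at most 1 of 6 is the same as at most 1 of the 5 further patients. The chance of acceptance is then

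A(p) = (1 − p)^5 + 5p(1 − p)^4,

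where p is the probability that a patient's DLT is observed. Assumptions, none from the documents: P is the true two-cycle DLT risk, and a fraction w of patients who are DLT-free after cycle 1 leave at that point and count as DLT-free.

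- Full observation (w = 0), P = 0.33: 0.67^5 + 5 × 0.33 × 0.67^4 = 0.135 + 0.332 = 0.468 (unrounded terms).
- Equal risk per cycle: q = 1 − √(1 − P), which is 0.1815 for P = 0.33 and 0.2929 for P = 0.50; p = q + (1 − q)(1 − w)q.
- Front-loaded, 80% of the risk in cycle 1: p = 0.8P + 0.2P(1 − w).

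| P | Timing of risk | p at w = 0 / 0.2 / 0.4 | A(p) at w = 0 / 0.2 / 0.4 |
|---|---|---|---|
| 0.33 | front-loaded | 0.330 / 0.317 / 0.304 | 0.468 / 0.494 / 0.521 |
| 0.33 | equal | 0.330 / 0.300 / 0.271 | 0.468 / 0.528 / 0.589 |
| 0.50 | front-loaded | 0.500 / 0.480 / 0.460 | 0.188 / 0.213 / 0.241 |
| 0.50 | equal | 0.500 / 0.459 / 0.417 | 0.188 / 0.244 / 0.308 |

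The increase is about 2.5 to 5.3 percentage points if risk is front-loaded and 5.6 to 12.1 points if it is equal per cycle.

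**4. Price of replacement.** On the 1 + 1 + 5 path, with an overall early-loss fraction L in the cohort of five, expected enrolment is 2 + 5/(1 − L): 7.6 at L = 10% and 10.3 at L = 40%, or 8 and 11 rounded up.

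**The case against.** **The plan does give a denominator.** It is patients treated, so a reader who infers that no counting rule exists at all goes too far. This stands. The problem is what the literal rule does when patients leave early, together with the absence of a replacement provision for cohort patients.

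**The two cycles may be meant to carry over.** The synopsis and sections 3.5, 5 and 12 speak of verification cohorts or groups in the plural. Section 3.6 says the MTD level is itself verified in five further patients, and the text scheme in section 10 says to continue as before. This wording allows that reading but does not state it. Even if it were accepted, it would not say how an early leaver is counted or whether a replacement may enter.

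**Two figures in sections 9 and 10 were not available for this review.** One may be the scheme to which section 9 refers. They could hold more detail. The text summary in section 10 contains no such rule, but it is condensed and so is only weak evidence about the figures.

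**Two stronger readings are tempting.** One is that the de-escalation cohort would be judged on a single cycle. No passage proposes this: the 21-day gate governs when the next verification patient enters, not when the MTD is declared. The other is that the gap favours a too-toxic dose in both cohorts. Under section 10 it does not, because in the verification group an incomplete patient holds escalation back.

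**The size rests on assumed rates.** This is true, and with front-loaded risk the shift is modest. The direction does not depend on the rates.

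**Conclusion.** The concern holds for the de-escalation cohort. The MTD and phase II dose are declared on five treated patients with no minimum observation, and early leavers count as DLT-free. Acceptance of a level with a 33% two-cycle DLT risk rises from 47% to between 49% and 59%. At 50% risk it rises from 19% to between 21% and 31%. These ranges assume that 20% to 40% of DLT-free patients leave after cycle 1, with either 80% or half of the risk weight in that cycle (the latter as equal per-cycle risk). The documents supply none of these rates, so the figures show the sensitivity of the rule and do not predict its behaviour in this trial.

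For the verification group the finding is narrower: section 10's rule is cautious but can leave the trial without a defined next step, and section 9 does not match it. A reader might also infer that the minimum of 7 is wrong. It is not; it reproduces as the shortest path if every patient is usable.

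**What to change.** Amend the wording of sections 9, 10 and 16.1.

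- Reconcile section 9 with section 10, and state one minimum DLT observation period for both cohorts. The sponsor should confirm whether it is the 2 cycles already used for the verification group.
- Define a cohort patient as DLT-evaluable if he or she had a DLT or completed that period at that level.
- Apply the criterion of at most 1 DLT in 5 further patients to 5 evaluable patients, and replace non-evaluable ones.
- Word section 9's limit of six per level as six evaluable patients; otherwise replacement would breach it.
- Keep counting DLTs from later cycles.
- State that the escalation patient enters the denominator of six under his or her own rule, usually one cycle at that level, so that the mix of exposures is explicit.
- Keep the minimum of 7 and label it 7 evaluable patients.

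**Cost.** A protocol amendment and a few replacement patients: about 8 to 11 expected on the 1 + 1 + 5 path at an assumed 10% to 40% early loss, with the minimum still 7. If the period is 2 cycles, one late replacement adds about 6 weeks (2 × 21 days). Each additional replacement adds about 3 weeks if the sequential-entry gate also applies to that cohort. Recruitment is planned for one year, so the timetable should be checked.

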Start 1 pt at 1 mg/m²/day with individual dose escalation at 0.5 mg/m²/day for 5 days every 3 weeks until any DLT (= dose "d1") or to a max of 8 cycles

Verification group (VG) of ≤5 further pts at d1 without indiv. dose esc.

(Verification group (VG) of ≤5 further pts at d1-0.5mg/m²/day without indiv. dose esc. in case a death occurs as DLT)

No further DLT in VG > resume dose escalation: start 1 pt of VG at d1 + 0.5 mg/m²/day (d), then as above

1 further DLT in VG > dose de-escalation d1 - 0.5 mg/m²/d, 5 further pts (d-1(-2))

>1 further DLT: d-1 = MTD

>1 further DLT > dose de-escalation, continue as above
```

Again, if a patient has been taken off the study due to a DLT or progressive disease, the patient may further be treated as follows. If the patient has stable disease or response and the DLT has been resolved, outside the study the patient may be treated

with the study medication on the highest tolerable dose level without DLT (§ 34 Declaration of Helsinki, Fortaleza 2013). In case of progressive disease or if the DLT has not been resolved, different treatment options are offered.

11. Study objectives and end-points

Primary Objectives

To evaluate the maximum tolerated dose (MTD) and the dose-limiting toxicity (DLT) of intravenously (i.v.) infused daily applications of tTF-NGR in patients with cancer (solid tumors and lymphomas), who had obtained all standard treatment known for their disease entity prior to entry on study.

Secondary Objectives

- 1. To determine the perfusion and vascular volume fraction of measurable tumor lesions versus normal reference tissue before and after tTF-NGR application by MRI as a imaging surrogate parameter for biological activity of the IMP.
- 2. To obtain pharmacokinetic data of tTF-NGR.

Primary Safety end-point

Maximum Tolerated Dose (MTD). MTD is the dose below the dose leading to reproducible episodes of Dose Limiting Toxicity (DLT) in at least 2/6 patients. DLT will be characterized by clinical, blood and serum monitoring at specified time points before and during study period.

Secondary Safety end-points

- 1. Occurrence and frequency of inhibition of tumor blood flow as measured by contrast-enhanced Magnetic Resonance Imaging (MRI).
- 2. Occurrence and frequency of tumor response defined as Complete Response (CR), Partial Response (PR), or Stabile Disease (SD) as defined by RECIST criteria.

Descriptive statistics will be used.

12. Patient evaluation and follow-up

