A first patient will be treated daily with tTF-NGR by 1-hour iv infusions for 5 days. Starting dose will be 1 mg/m²/day, intraindividual dose-escalation will be performed in 0.5 mg/m²/day steps upon a rest period of 16 days for the next treatment cycle of 5 days in this patient. If diagnosed with progressive disease (PD) after 2 cycles or clinically as judged by the investigator even before, this patient will go off study and will be replaced by a further patient in whom individual dose escalation will be resumed. Upon occurrence of DLT up to 5 further patients will be treated at this specific dose in a verification cohort. Further procedure such as de-escalation and definition of MTD and dose level recommended for further clinical trials will be performed as described above. Thus, a minimum number of patients to reach objectives of this study are envisaged as being 7 patients. This number of patients represent 1 patient for first dose-escalation with DLT at the highest dose, starting the verification cohort and reproduction of DLT in the first patient (of up to 5 patients) of the verification cohort, de-escalation with -0.5 mg/m 2 /day in 5 further patients with \leq 1 additional DLT.

Possible higher numbers of patients in situations such as with no additional DLT in the verification group and further dose-escalation is possible, but cannot be determined before the study with confidence.

17. Study duration, Premature Termination of the Study

Planned start date of the study (FPFV, first patient first visit): 01.11.2016

Planned end date of recruitment (LPFV, last patient first visit): 01.11.2017

Planned end date of the study: 01.05.2018

Planned duration of single patient participation: according to occurrence of DLT and antitumor activity

Planned duration of recruitment: 01.11.2016 - 01.11.2017

Planned overall duration of the study: 01.11.2016 - 01.05.2018

Planned duration of follow up of individual patients within study: 3 months

Definition of the End of the Study

To allow reasonable time for evaluation and report, the end of study is plannned to be at "last patient last visit" (LPLV).

Premature Study Termination

Premature Termination of Study Participation of a Single Patient

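### Below the starting dose the level has five patients, not six, so one DLT in five meets the MTD rule while the ≤1/6 definition is still undecided

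*Combined protocol and SAP*

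**What the plan says.** Section 10 gives an operative rule for ending de-escalation. It continues until "≤1 DLT occurs in 5 further patients treated on a specific dose-level, i.e. there are ≤1/6 patients with DLT in total" on that level. The consequence follows at once: "This dose level is declared the MTD and will be recommended for further studies". Section 9 pairs the same two conditions.

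Section 10 also gives a definition. Any dose with DLT in at most 1/6 "patients is defined to be the MTD, if on the next higher dose level the observed number of patients with DLT is" at least 2/6. The primary safety endpoint in Section 11 agrees: "MTD is the dose below the dose leading to reproducible episodes of Dose Limiting Toxicity (DLT) in at least 2/6 patients".

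The starting dose is 1 mg/m²/day and the step is 0.5 mg/m²/day. If a DLT occurs at the start or one step above it, Section 10 says that "further dose de-escalation below the starting dose level can be performed as described to establish MTD". With these steps, the only level below the start is 0.5 mg/m²/day.

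Three rules determine who can have been treated at a given level:
- An escalation patient with a DLT is taken off study (Section 10). Later dosing at a lower level is off-study compassionate use.
- Section 8 states: "De-escalation in individual patients in dosing is not allowed during the Study Period".
- A replacement escalation patient resumes "starting with the highest dose level reached without DLT in the previous patient" (Section 10), and so never below 1 mg/m²/day.

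**The concern.** The rule counts five new patients and the definition counts six. They coincide when one escalation patient has already passed through the level without a DLT, because 1 + 5 = 6. Below the starting dose no such patient exists on the non-fatal path. The rule carried down to 0.5 mg/m²/day is therefore a five-patient rule, although the text describes it as a six-patient one.

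The MTD is the primary endpoint and becomes the recommended phase II dose. At 0.5 mg/m²/day the rule as written is easier to pass than the definition it is meant to implement, and a report could state ≤1/6 when five patients were treated. If this branch is ever reached, it will be because DLTs were seen at or near the starting dose, so the criterion should be unambiguous there.

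**Working it through.** **The plan's own figure.** Section 16.1 counts one escalation patient with DLT, then "reproduction of DLT in the first patient (of up to 5 patients) of the verification cohort", then five patients one step lower with at most one further DLT: 1 + 1 + 5 = 7. The stated minimum of 7 is reproduced.

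**Patients per level.** These counts take the non-fatal path with one escalation patient, the second DLT in the first verification patient, and all five further patients treated at each lower level.

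| First DLT at (mg/m²/day) | Patients at 2.0 | at 1.5 | at 1.0 | at 0.5 |
|---|---|---|---|---|
| 1.0 | – | – | 1 + 1 = 2 | 0 + 5 = 5 |
| 1.5 | – | 1 + 1 = 2 | 1 + 5 = 6 | 0 + 5 = 5 |
| 2.0 | 1 + 1 = 2 | 1 + 5 = 6 | 1 + 5 = 6 | 0 + 5 = 5 |

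At every de-escalation level from 1.0 upwards the total is six and the stated equivalence holds. At 0.5 the total is five whichever route leads there.

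**What each result at 0.5 means.**

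| DLTs in the five | Operative rule (≤1 in five) | Definition (≤1/6 or ≥2/6) |
|---|---|---|
| 0 | MTD | A sixth patient could give at most 1/6: MTD |
| 1 | MTD | 1/6 or 2/6, depending on the sixth patient: undecided |
| 2 or more | Not MTD | Already at least 2: not MTD |

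Only 1/5 separates the two. It is an observed rate of 20%, against 16.7% for 1/6.

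**Size, given that 0.5 is reached.** The documents state no DLT rate, so the true rate p at 0.5 is an assumption, shown over a range. Patients are taken as independent.

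- P(≤1 of 5) = (1−p)⁵ + 5p(1−p)⁴
- P(≤1 of 6) = (1−p)⁶ + 6p(1−p)⁵
- Difference = P(exactly 1 of 5) × p = 5p²(1−p)⁴

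For p = 0.20: P(≤1 of 5) = 0.328 + 0.410 = 0.737, and P(≤1 of 6) = 0.262 + 0.393 = 0.655. The difference is 0.410 × 0.20 = 0.082.

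| Assumed p | P(≤1 of 5) | P(≤1 of 6) | Difference |
|---|---|---|---|
| 0.10 | 0.919 | 0.886 | 0.033 |
| 0.20 | 0.737 | 0.655 | 0.082 |
| 0.30 | 0.528 | 0.420 | 0.108 |
| 0.40 | 0.337 | 0.233 | 0.104 |

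The difference is the chance that 1/5 is accepted when a sixth patient would have turned it into 2/6.

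**The case against.** **The sentence can be read as requiring six.** Both conditions stand in one sentence, and de-escalation below the start is to follow the described procedure, which includes the ≤1/6 condition. A careful team could treat a sixth patient after 1/5. That is fair, and a reader should not infer that 1/5 is bound to end the trial at 0.5. But the number of further patients is stated as five, and no visible sentence adds a sixth. This reading confirms that the text conflicts with itself at this level; it does not remove the conflict.

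**The patient who tolerated 1.0 could be credited at 0.5.** If the first DLT was at 1.5 or higher, a monotone dose–toxicity assumption would allow this. The protocol does not state that assumption, and the argument is unavailable when the first DLT occurs at 1.0.

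**Figures are missing from the text reviewed.** One belongs to Section 9 and one to Section 10, and either might give 0.5 its own rule. Nothing in the visible text suggests so, and the prose would still say five. This should be checked against the full document.

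**The branch is remote.** This stands. The protocol itself calls it very unlikely. Sections 3.2 and 14 report first-in-man doses up to 4 mg/m² as well tolerated; 0.5 is one eighth of that. That experience was with weekly rather than five daily infusions, so it does not transfer directly, but it makes the 30% and 40% rows pessimistic.

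**Conclusion.** The point holds and is minor. On the non-fatal path, 0.5 mg/m²/day has five patients, the equivalence stated in Section 10 fails there, and 1/5 meets the rule for declaring the MTD while the six-patient definition is undecided. Given that 0.5 is reached, the rule is more lenient than the definition by about 3, 8, 11 and 10 percentage points at assumed DLT rates of 10, 20, 30 and 40%.

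A reader might infer three stronger conclusions that the documents do not support:
- *That the trial as a whole has a material chance of recommending too toxic a dose.* The figures above are conditional. The chance of reaching 0.5 depends on DLT rates at 1.0 and above, which are not given, and on every de-escalation route, including those starting at 2.0 or higher. No unconditional probability should be quoted.
- *That the equivalence is wrong throughout.* With one escalation patient it is correct at de-escalation levels of 1.0 mg/m²/day and above.
- *That the minimum of 7 patients is wrong.* It reproduces exactly and is unaffected.

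The fatal-DLT path has its own rules and is not part of this conclusion.

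**What to change.** Add one sentence to Section 10: *For a level that no escalation patient has passed through, if exactly 1 of the 5 further patients has a DLT, a sixth patient is treated before the MTD is declared.* The decision at 0.5 mg/m²/day then matches the definition in Sections 10 and 11.

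The cost is at most one extra patient, and only after 1/5 on this branch. The shortest route ending at 0.5 with such a result would take 1 + 1 + 6 = 8 patients; with 0/5 it stays at 7.

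If a sixth patient is not wanted, state the criterion for such a level as ≤1/5 and report it in that form. This needs no extra patient, but it accepts a more lenient criterion at that level than elsewhere.

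### Section 9's stop rule does not exempt the verification group treated one level lower after a fatal DLT; read literally, it lowers the next dose where Section 10 returns to the fatal dose

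*Combined protocol and SAP*

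**What the plan says.** **Section 9** sets the verification group after a first DLT: up to 5 more patients at the same level, "or in case of deadly DLT in the dose level below (verification group for DLT; maximum of 6 patients on this level"). It then gives a stop rule: "Upon observation of one more episode of any DLT within the verification group, patient accrual to this verification group is stopped". Accrual "is stopped with this second patient with DLT and de-escalation by a" 0.5 mg/m²/day step follows, with 5 further patients at the lower dose. De-escalation ends when at most 1/6 "patients in total with DLT on this dose level (scheme see below"). The stop rule is not restricted to a non-fatal first DLT.

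**Section 10** separates the two cases. The ordinary track is conditional: "If this first observed DLT is nonfatal, up to 5 more patients will then be treated on the same dose level". For the other case it says: "If an observed DLT is fatal, the above dose escalation scheme is modified". The next patients then go to d_fatal − 0.5. If at that level "no DLT or not more than 1 DLT is observed that is non-fatal, further patients are treated on the dose level" d_fatal, this continues "until any further DLT is observed or 6 patients are included on this dose level in total". A following sentence requires possible later escalation to a level with a death to be discussed with the data safety board.

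**MTD.** Section 10 defines it as a dose with DLT in at most 1/6 patients when the next higher level has at least 2/6. Section 9 defines it as the dose below the lowest level with reproducible DLT.

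**Section 3.6** also places the cohort one level lower after a death and refers forward for the exact scheme.

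**The concern.** Suppose the first DLT is fatal and exactly one of the five verification patients at d_fatal − 0.5 then has a non-fatal DLT. That patient is the second patient with a DLT in the trial, and the event is one more DLT within the verification group. On its words, Section 9's stop rule is met and the dose goes down. Section 10 takes the same observation as permission to go back up.

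The investigator would have to choose between the two texts just after a treatment-related death. The choice sets the dose of the next patients and also the declared MTD, which Section 10 carries forward as the recommended phase II dose.

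**Working it through.** **1. The plan's own figure.** Section 16.1 gives a minimum of 7 patients: 1 (first DLT) + 1 (second DLT) + 5 (one step lower) = 7. This reproduces. The shortest contested path is also 7 under either section (Section 9: 1 + 1 + 5; Section 10: 1 + 5 + 1), so the sample-size statement is not affected.

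**2. Tracing the rules after a fatal first DLT.**

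| DLTs at d_fatal − 0.5 | Section 9, literal | Section 10 |
|---|---|---|
| 0 | escalation may resume | d_fatal |
| exactly 1, non-fatal | d_fatal − 1.0 | d_fatal |
| 2 or more | down | down |

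Only the middle row conflicts in direction. The gap in next dose is d_fatal − (d_fatal − 1.0) = 1.0 mg/m²/day. Section 9 would act at the first DLT in the group, without waiting for all five patients.

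**3. Consequence for the MTD.**
- Section 9 path: d_fatal − 1.0 or lower.
- Section 10 path: d_fatal − 0.5 if a further DLT occurs at d_fatal, otherwise not below d_fatal (leaving aside DLTs in cycle 3 or later).

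At the decision, d_fatal has one DLT and d_fatal − 0.5 has one. Declaring d_fatal − 1.0 the MTD would therefore not meet Section 10's own requirement of at least 2/6 on the next higher level.

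**4. How often the branch arises.** The documents give no DLT rates, so these are assumptions. With DLT rate p at d_fatal − 0.5 and five patients, P(exactly one) = 5p(1 − p)⁴. If a share f of all DLTs is fatal, then, given that a first DLT occurs, the joint probability of a fatal first DLT and exactly one non-fatal DLT in the group is f(1 − f) × 5p(1 − p)⁴.

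| p | P(exactly one) | joint, f = 0.10 (× 0.09) | joint, f = 0.25 (× 0.1875) |
|---|---|---|---|
| 0.10 | 0.328 | 0.030 | 0.062 |
| 0.20 | 0.410 | 0.037 | 0.077 |
| 0.25 | 0.396 | 0.036 | 0.074 |
| 0.33 | 0.332 | 0.030 | 0.062 |

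The joint probability is about 3% to 8%.

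**5. What follows once it has arisen.** On the Section 10 path, up to 5 more patients are treated at d_fatal until a further DLT. With true rate q there, P(further DLT) = 1 − (1 − q)⁵ and the expected number dosed is [1 − (1 − q)⁵]/q.

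| q | P(further DLT), so MTD = d_fatal − 0.5 | expected patients at d_fatal |
|---|---|---|
| 0.20 | 0.67 | 3.4 |
| 0.33 | 0.86 | 2.6 |
| 0.50 | 0.97 | 1.9 |

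On the literal Section 9 path, no further patient receives d_fatal. The MTD is d_fatal − 1.0 if at most 1 of 5 has a DLT there: probability 0.92 at a rate of 0.10 and 0.74 at 0.20. Otherwise it is lower.

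**The case against.** The strongest reply is that the protocol already settles the matter in favour of Section 10, and most of that reply stands.

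- Section 10 says the scheme above it is modified for a fatal DLT, and its same-level group is limited to a non-fatal first DLT. The general stop rule is repeated in Section 10 shortly before the paragraph that modifies it.
- Sections 3.6 and 9 both point forward, and Section 10 is the section on escalation and de-escalation.
- Section 9's MTD definition and its 1/6 end condition count per level. On that count, one DLT at d_fatal − 0.5 is acceptable, and nothing has been reproduced on either level.

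What does not fall away is that Section 9 has its own clause for a fatal DLT and then applies the stop rule without an exception. Counting the second patient across levels is the plain sense of that sentence, even if it is not the intended sense.

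A reader might also infer that the summary scheme in Section 10 backs the Section 9 path. It does not. Its step down to d1 − 0.5 is where the fatal-case group already is, and its step up to d1 + 0.5 starts from a group at d1. Those boxes describe the non-fatal track only. Two figures near these rules are not reproduced in the text available, so they cannot be used on either side.

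**Conclusion.** Section 9's stop rule is wrong as written for a fatal first DLT followed by exactly one non-fatal DLT one level lower. It gives a next dose 1.0 mg/m²/day below Section 10's and a lower MTD. It should be fixed; confidence is moderate, because Section 10 very likely governs and a per-level reading of Section 9 removes the conflict.

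The 3% to 8% rests on assumed DLT rates and fatal shares, and on five patients treated at the lower level. The larger percentages in the last part of the working apply only after that branch has been entered.

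Three stronger readings are tempting and not supported:
- That the two sections are in open, unresolved contradiction. Section 10's statement that it modifies the scheme argues against this.
- That any return to d_fatal is the defect. After 0 DLTs both sections permit upward movement, and Section 10 calls for a data safety board discussion.
- That the plan needs an MTD rule for a refusal by the board. Section 10 requires only discussion, and Section 12.4.1 gives the board an advisory role, so no power of refusal is shown.

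**What to change.** 1. **Section 9:** limit the stop rule on a further DLT in the verification group to a non-fatal first DLT, and add: *After a fatal DLT the rule in Section 10 applies.*
2. **Section 10:** in the sentence on the data safety board, delete the word *later* and state that the discussion takes place before any further patient is dosed at d_fatal.
3. **Summary scheme in Section 10:** add the fatal branch, showing what follows each outcome at d_fatal − 0.5.

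The cost is a wording amendment, with no added patients or procedures and no change to the minimum of 7. If the amendment is classed as substantial, Section 22 requires a favourable ethics committee opinion and competent authority approval before it is implemented.
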